2.1.2.5 HIV-positive participants

2.1.2.6 Pregnant participants- a pregnancy test (urine or serum) with a sensitivity of 25 mIU/mL must be done at screening.

2.1.2.7 Participants with second malignancies requiring active systemic therapy are excluded.

2.1.2.8 Class 3 or 4 congestive heart failure as defined by the New York Heart Association Functional Classification

- 2.1.2.9 History of any ventricular arrhythmia
- 2.1.2.10 Unable to swallow capsules, or disease significantly affecting gastrointestinal function, or resection of the stomach or small bowel, or symptomatic inflammatory bowel disease or ulcerative colitis, or partial or complete bowel obstruction.
- 2.1.2.11 Uncontrolled ongoing or active infection
- 2.1.2.12 Concomitant use of warfarin or other vitamin K antagonists
- 2.1.2.13 Known bleeding disorders (e.g., von Willebrand's disease) or hemophilia.
- 2.1.2.14 Currently active, clinically significant hepatic impairment ( $\geq$  moderate hepatic impairment according to the NCI/Child Pugh classification ([Appendix B](#)))
- 2.1.2.15 Uncontrolled intercurrent illness or psychiatric illness/social situations that would limit compliance with study requirements.

### 2.1.3 Recruitment strategies

Study participants will be recruited from the population of participants screened in the lymphoid malignancies clinic of the National Institutes of Health. These will include both referrals from outside physicians as well as participant self-referrals. This protocol may be abstracted into a plain language announcement posted on NIH websites, including clinicaltrials.gov and the CCR website, and on NIH social media platforms.

## 2.2 SCREENING EVALUATION

### 2.2.1 Screening activities performed prior to obtaining informed consent

Minimal risk activities that may be performed before the participant has signed a consent include the following:

- Email, written, in person or telephone communications with prospective participants
- Review of existing medical records to include H&P, laboratory studies, etc.
- Review of existing MRI or CT images
- Review of existing photographs or videos
- Review of existing pathology specimens/reports from a specimen obtained for diagnostic purposes

### 2.2.2 Screening activities performed after a consent for screening has been signed

The following activities will be performed only after the participant has signed this study consent. Assessments performed at outside facilities or on another NIH protocol within the timeframes below may also be used to determine eligibility once a participant has signed the consent.

Assessments and procedures to confirm study eligibility should be completed within 28 days prior to treatment initiation (unless otherwise noted).

#### 2.2.2.1 Clinical Assessments

- Medical history, including diagnosis, treatment (e.g., systemic treatments, radiation, and surgeries), status, and significant prior/ongoing side effects and symptoms

- Physical examination, including weight, vital signs (i.e., temperature, pulse, respiratory rate, and blood pressure); and, assessment of performance status using the ECOG scale
- Review of concomitant medications

#### 2.2.2.2 Laboratory Evaluations

- CBC with differential
- Chemistry panels including: Acute Care Panel (Sodium (NA), Potassium (K), Chloride (CL) Total CO2 (Bicarbonate), Creatinine, Glucose, Urea nitrogen, eGFR); Mineral Panel (Albumin, Calcium, Magnesium, Phosphorus); Hepatic Panel (Alkaline Phosphatase, ALT/GPT, AST/GOT, Total Bilirubin, Direct Bilirubin); and, 24-hour urine creatinine clearance (if needed to measure CrCl in cases where serum creatinine >1.5 mg/dl)
- Coagulation panel, including PT and aPTT
- HIV 1 /2 antibody, Hepatitis B surface antigen (HBsAg), Hepatitis B surface antibody (HBsAb), Hepatitis B core antibody (HBcAb), and Hepatitis C antibody (HCV Ab)
  - Participants who are HBsAg negative and HBcAb positive or HBsAg positive will have viral load testing by HBV PCR.
  - Participants who are HCV Ab positive will have viral load testing by HCV PCR.
- Urine and/or serum HCG in IOCBP (within 14 days prior to initiation of study treatment)
  - A pregnancy test (urine or serum) with a sensitivity of 25 mIU/mL must be done in accordance with Celgene Revlimid REMS™ guidelines for individuals of childbearing potential (IOCBP) only.

#### 2.2.2.3 Imaging Studies

- CT chest, abdomen, and pelvis (C/A/P) (with IV and PO contrast unless contraindicated)
- MRI brain
- F FDG-PET brain and body (must be performed at NIH)

#### 2.2.2.4 Other Assessments and Procedures (within 14 days prior to treatment unless otherwise stated)

- Pathologic review of archival sample for confirmation of B-cell lymphoma by Laboratory of Pathology, NCI (no time limit). If the sample is not available, and there is an accessible tumor, a biopsy will be done to confirm the diagnosis.
- Lumbar puncture/Ommaya tap for CSF studies including protein, glucose, cell count/differential, cytology, and flow cytometry for confirmation of CNS involvement
- Electrocardiogram (EKG)
- Confirmation of registration to Revlimid REMS™ program

## 2.3 PARTICIPANT REGISTRATION AND STATUS UPDATE PROCEDURES

Registration and status updates (e.g. when a participant is taken off protocol therapy and when a participant is taken off-study) will take place per CCR SOP ADCR-2, CCR Participant Registration & Status Updates found at:

[https://nih.sharepoint.com/sites/NCI-CCR-OCD-Communications/SitePages/OEC-Administrative---Clinical-Research-\(ADCR\).aspx?Mode=Edit](https://nih.sharepoint.com/sites/NCI-CCR-OCD-Communications/SitePages/OEC-Administrative---Clinical-Research-(ADCR).aspx?Mode=Edit)

### 2.3.1 Screen Failures

Screen failures are defined as participants who consent to participate in the clinical trial but are not subsequently assigned to the study intervention. A minimal set of screen failure information is required to ensure transparent reporting of screen failure participants, to meet the Consolidated Standards of Reporting Trials (CONSORT) publishing requirements and to respond to queries from regulatory authorities. Minimal information includes demography, screen failure details, eligibility criteria, and any serious adverse event (SAE).

Individuals who do not meet the criteria for participation in this trial (screen failure) because of a laboratory abnormalities may be rescreened. Only SAEs occurring after the administration of an investigational agent will be reported to the Sponsor. SAEs will be reported to IRB as required.

### 2.3.2 Treatment Assignment Procedures

#### 2.3.2.1 Cohorts

Number	Name	Description
1	CNS lymphomas	Participants with primary diffuse large B-cell lymphoma of the CNS (PCNSL) or secondary CNS lymphoma (SCNSL)

#### 2.3.2.2 Arms

Number	Name	Description
1	Experimental- lenalidomide + nivolumab window; followed by VIPOR-Nivo (Closed on 06/06/2022)	Nivolumab on day 1 with lenalidomide (days 1-14) for a 21-day cycle. Following Window, VIPOR-Nivo (venetoclax, ibrutinib, prednisone, obinutuzumab, lenalidomide, and nivolumab) in 21-day cycles for up to 6 cycles
2	Experimental- VIPOR	VIPOR (venetoclax, ibrutinib, prednisone, obinutuzumab, and lenalidomide) in 21-day cycles for up to 6 cycles

**\*NOTE:** participants with CrCl >60 mL/min will receive lenalidomide 15mg (dose level 1) while those with CrCl >40 mL/min and <60mL/min will receive lenalidomide 10mg (dose level -1) (Table 3).

#### 2.3.2.3 Arm Assignment

In the original study design, participants in Cohort 1 were directly assigned to Arm 1. After 4 participants were enrolled, that arm was closed to further accrual on 06/06/22. All participants will now be assigned to Arm 2.

## **2.4 BASELINE EVALUATION**

The baseline evaluations should be performed within 14 days prior to the first dose of the study treatment unless otherwise noted; tests performed as part of screening do not need to be repeated if they were performed within the specified window prior to initiation of study therapy. See the Study Calendar ([Appendix D](#)) for details.

## **3 STUDY IMPLEMENTATION**

**NOTE:** The original study design included nivolumab, i.e., VIPOR-Nivo, for up to 6 cycles with an initial treatment window of lenalidomide with nivolumab alone. Due to safety concerns, study enrollment was suspended after enrollment of 4 participants, and re-designed as is reflected below.

[figure not shown]
### **3.1 STUDY DESIGN**

This is a non-randomized, open-label, single institution study evaluating the combination of VIPOR regimen in up to 16 participants with CNSL (PCNSL and SCNSL). Participants may undergo optional fresh tumor research biopsies prior to treatment and at the time of progression wherever feasible. In patients without an Ommaya catheter, this may be placed prior to the start of therapy but is not required for treatment. The study treatment will assess the safety, tolerability, and efficacy of VIPOR in CNSL which may continue for up to 6 cycles, or until one of the criteria in Section [3.8.1](#) applies.

Treatment should be delivered on an outpatient basis in most situations. Treatment can be delivered on an inpatient basis for other reasons clearly documented in the medical record (preplanned decision for increased monitoring, convenience, or collection of correlative samples).

Participants will be restaged regularly as explained in the Study Calendar ([Appendix D](#)) and followed for up to 10 years.

### 3.1.1 Study Schema

## 3.2 DRUG ADMINISTRATION

After enrollment participants will proceed to induction therapy. A maximum of 6 cycles of induction therapy will be given every 21 days with the following dosing schedule:

- Obinutuzumab 1000 mg IV rate escalated infusiona on days 1 and 2
- Prednisone 100 mg PO daily days 1-7 (approximately 30-60 minutes prior to obinutuzumab infusion on days 1 and 2)
- Ibrutinib 560 mg PO daily days 1-14
- Lenalidomide 15 mg PO daily days 1-14 (if CrCl > 60 mL/min) or 10 mg PO daily days 1-14 (if CrCl < 60 mL/min but > 40 mL/min)
- Venetoclax 800 mg PO daily on days 1-14
- Acetaminophen 650 mg PO daily on days 1 and 2 (approximately 30-60 minutes prior to Obinutuzumab infusion)
- Diphenhydramine 50 mg PO daily on days 1 and 2 (approximately 30-60 minutes prior to Obinutuzumab infusion)
- Peg-filgrastim 6 mg subcutaneous once on day 8 only

a Obinutuzumab infusion starting at 50 mg/hr with rate increase by 50 mg/hr every 30 minutes as tolerated to a maximum rate of 400 mg/hr. If tolerated, subsequent infusions may start at 100 mg/hr with rate increase by 100 mg/hr every 30 minutes to a maximum rate of 400 mg/hr. Monitor participants closely for signs/symptoms of the infusion reaction and interrupt/discontinue infusion for any signs of a reaction and contact the investigator.

For more details see Section [14](#)

### 3.3 DOSE MODIFICATIONS AND DOSE DELAYS

The following sections detail dose modifications guidelines for each individual drug of the VIPOR regimen based on documented toxicity. Dose reductions for multiple study agents based on the same toxicity is not necessary and dosing should be modified only for the most likely offending agent identified.

#### 3.3.1 Criteria for Starting a New Cycle of Study Therapy

A new course of study treatment may begin on Day 1 of a new cycle if:

- ANC  $\geq$  1000/ $\mu$ L and
- Platelet count  $\geq$  50,000/ $\mu$ L and
- CrCl  $>$  40 mL/min
- No drug-related  $\geq$  Grade 3 toxicity

If the criteria are not met, assessments may be repeated after 1 week. The initiation of a new cycle of study therapy should be delayed until participant meets criteria to receive study drug as planned.

A dose delay of up to 6 weeks from the planned start of an induction cycle is permitted to allow recovery of toxicities. Actions for recurrent hematologic adverse events are described in the tables for each drug in the sections below (lymphopenia is not considered a hematologic toxicity, as it is an expected outcome of therapy). If treatment is delayed for more than 6 weeks, the participant should be withdrawn from the study treatment.

If one of the study drugs is discontinued because of toxicity as addressed below, participant will continue treatment with other drugs. If two or more drugs are discontinued, participants will be taken off study treatment.

#### 3.3.2 Dose Modifications for Venetoclax and Obinutuzumab

Sample guidelines for dose delay and modification of venetoclax when paired with obinutuzumab are shown in [Table 1](#). These guidelines pertain to dose delays and modifications based on physical examination findings, observed toxicities, and laboratory results obtained within 72 hours before study treatment administration.

No dose modifications of obinutuzumab are allowed. Venetoclax dose may be re-escalated (even to the full dose) at the discretion of the investigator. See [Table 2](#) for the dose levels for venetoclax dose reduction.

For non-hematologic toxicities, dosing of study therapy may be resumed upon resolution to Grade  $\leq$  1 or baseline status.

**Table 1: Sample Guidelines for Dose Delay or Modification of Venetoclax when given with Obinutuzumab and Combination Targeted Therapy**

Event(s)	Dose Delay or Modification
Neutropenia: 
 
Grade 3 (ANC <1,000/<math>\mu</math>L for <math>\geq</math> 7 days, OR
 
Grade 4 (ANC <500/<math>\mu</math>L for any duration
 
	
 
Hold venetoclax.
 
Administer growth factors (e.g., G-CSF for neutropenia as indicated).                     
 
-If ANC < 1000/<math>\mu</math>L for <math>\leq</math> 7 days, administer full dose of study treatment for the next cycle.
 
-If ANC < 1000/<math>\mu</math>L for <math>></math> 7 days, reduce the dose of venetoclax by 1 dose level.
 
 
 
For subsequent episodes, dose reduction 2 of venetoclax and drug discontinuation will be considered.
 
If the primary cause of neutropenia is thought to be lymphoma infiltration into the bone marrow, the Principal investigator may elect not to reduce the dose of venetoclax .
 

Febrile neutropenia or neutropenia with infection	
 
Hold venetoclax and obinutuzumab until resolution.
 

Thrombocytopenia: 
 
Grade 3 (decrease to <50,000/ <math>\mu</math>L) associated with <math>></math> Grade 2 bleeding, OR
 
Grade 4 (decrease to <25,000/ <math>\mu</math>L) with or without bleeding
 
	
 
Hold venetoclax.                     
 
-If platelet count < 50,000/<math>\mu</math>L for <math>\leq</math> 7 days, administer full dose of study treatment for the next cycle.
 
-If platelet count < 50,000/<math>\mu</math>L for <math>></math> 7 days, reduce the dose of venetoclax by 1 dose level.
 
 
 
For subsequent episodes, dose reduction 2 of venetoclax and drug discontinuation will be considered.
 

Severe thrombocytopenia (platelets < 10,000/ $\mu$ L) and/or symptomatic bleeding in participants who are not receiving concomitant anticoagulants or platelet inhibitors	
 
Hold obinutuzumab in case of severe thrombocytopenia (platelets < 10,000/<math>\mu</math>L) or symptomatic bleeding (irrespective of platelet count) until it resolves.
 

Thrombocytopenia with platelets < 20,000/ $\mu$ L and/or symptomatic bleeding in participants who are receiving concomitant anticoagulants or platelet inhibitors a,b	
 
Hold obinutuzumab in case of platelets < 20,000/<math>\mu</math>L or symptomatic bleeding (irrespective of platelet count) until it resolves.                     
 
-For participants who are receiving concomitant anticoagulant when thrombocytopenia with platelets < 20,000/<math>\mu</math>L develops, adjust the dose or hold the drug per investigator discretion.a
 
-For participants who are on platelet inhibitors when thrombocytopenia with platelets < 20,000/<math>\mu</math>L develops, consider temporarily holding their use.b
 
 
 

Grade 1 or 2 neutropenia and/or thrombocytopenia	
 
No dose reduction or delay.
 

Event(s)	Dose Delay or Modification
Any other Grade 4 toxicity or unmanageable Grade 3 toxicity attributed to venetoclax	
 
Hold venetoclax.                     
 
-If improves to <math>\leq</math> Grade 2 in <math>\leq</math> 7 days, administer full dose of study treatment for the next cycle.
 
-If improves to <math>\leq</math> Grade 2 in <math>></math> 7 days, reduce the dose of venetoclax by 1 dose level.
 
 
 
For subsequent episodes, dose reduction 2 of venetoclax and drug discontinuation will be considered.
 

ANC = absolute neutrophil count; G-CSF = granulocyte colony-stimulating factor.

a If the participant's clinical condition requires the use of concomitant anticoagulants, the participant is at increased risk of bleeding when thrombocytopenia with platelets  $<$  20,000/ $\mu$ L develops.

b Clinical decision-making may be adjusted depending on the participant-specific assessment of benefit and risk

**Table 2: Venetoclax Dose Reduction**

Dose Reduction	Venetoclax Dose
1	600 mg
2	400 mg

### 3.3.3 Dose Modifications for Ibrutinib

Sample guidelines for dose delay and modification of ibrutinib are shown in **Table 3**. At the discretion of investigator, dose-modification guidelines should be evaluated and revised, as appropriate, based on the risk associated with the regimen employed. See **Table 4** for the dose levels for ibrutinib dose reduction.

**Table 3: Guidelines for Dose Delay or Modification of Ibrutinib**

Event(s)	Dose Delay or Modification
Neutropenia: 
 
Grade 3 (ANC <math><</math> 1,000/<math>\mu</math>L for <math>\geq</math> 7 days, OR
 
Grade 4 (ANC <math><</math> 500/<math>\mu</math>L for any duration)
 
	
 
Hold ibrutinib.
 
Administer growth factors (e.g., G-CSF for neutropenia as indicated).                             
 
-If ANC <math><</math> 500/<math>\mu</math>L for <math>\leq</math> 7 days, administer full dose of study treatment for the next cycle.
 
-If ANC <math><</math> 500/<math>\mu</math>L for <math>></math> 7 days, reduce the dose of ibrutinib by 1 dose level.
 
 
 
For subsequent episodes, dose reduction 2 of ibrutinib and drug discontinuation will be considered.
 
If the primary cause of neutropenia is thought to be lymphoma infiltration into the bone marrow, the Principal investigator may elect not to reduce the dose of ibrutinib.
 

Event(s)	Dose Delay or Modification
Febrile neutropenia or neutropenia with infection	
 
Hold ibrutinib until resolution.
 

Thrombocytopenia: 
 
Grade 3 (decrease to <50,000/ <math>\mu</math>L) associated with > Grade 2 bleeding, OR
 
Grade 4 (decrease to <25,000/ <math>\mu</math>L) with or without bleeding
 
	
 
Hold ibrutinib.                             
 
If platelet count < 50,000/<math>\mu</math>L for <math>\leq</math> 7 days, administer full dose of study treatment for the next cycle.
 
If platelet count < 50,000/<math>\mu</math>L for > 7 days, reduce the dose of ibrutinib by 1 dose level.
 
 
 
For subsequent episodes, dose reduction 2 of ibrutinib and drug discontinuation will be considered.
 

Grade 1 or 2 neutropenia and/or thrombocytopenia	
 
No dose reduction or delay.
 

Grade 3 or 4 nausea, vomiting, or diarrhea if persistent, despite optimal anti-emetic and/or anti-diarrheal therapy	
 
Hold ibrutinib.                             
 
If improves to <math>\leq</math> Grade 2 in <math>\leq</math> 7 days, administer full dose of study treatment for the next cycle.
 
If improves to <math>\leq</math> Grade 2 in > 7 days, reduce the dose of ibrutinib by 1 dose level.
 
 
 
For subsequent episodes, dose reduction 2 of ibrutinib and drug discontinuation will be considered.
 

Grade 3 or 4 atrial fibrillation/flutter or persistent atrial fibrillation/flutter of any grade	
 
Hold ibrutinib.
 
Initiate medical management of atrial fibrillation/flutter.
 
Consider the risks and benefits of restarting ibrutinib treatment. If clinically indicated, the use of anticoagulants or antiplatelet agents may be considered for the thromboprophylaxis of atrial fibrillation.
 

Any other Grade 4 toxicity or unmanageable Grade 3 toxicity attributed to ibrutinib	
 
Hold ibrutinib.                             
 
If improves to < Grade 2 in < 7 days, administer full dose of study treatment for the next cycle.
 
If improves to < Grade 2 in > 7 days, reduce the dose of ibrutinib by 1 dose level.
 
 
 
For subsequent episodes, dose reduction 2 of ibrutinib and drug discontinuation will be considered.
 

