**Table 4: Ibrutinib Dose Reduction**

Dose Reduction	Ibrutinib Dose
1	420 mg
2	280 mg

Please see Section 4.2.1 for guidelines for management of ibrutinib in participants who require treatment with a strong CYP3A inhibitor.

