**Table 5: Guidelines for Dose Delay or Modification of Lenalidomide**

Event(s)	Dose Delay or Modification during a cycle
Neutropenia: • Grade 3 (ANC <1,000/ $\mu$ L) for $\geq$ 7 days, OR • Grade 4 (ANC <500/ $\mu$ L) for any duration	

Hold lenalidomide.

Administer growth factors (e.g., G-CSF for neutropenia as indicated).

-If ANC < 1000/<math>\mu</math>L for <math>\leq</math> 7 days, administer full dose of study treatment for the next cycle.

-If ANC < 1000/<math>\mu</math>L for <math>></math> 7 days, reduce the dose of lenalidomide by 1 dose level.

For subsequent episodes, dose reduction 2 of lenalidomide and drug discontinuation will be considered.

If the primary cause of neutropenia is thought to be lymphoma infiltration into the bone marrow, the Principal investigator may elect not to reduce the dose of lenalidomide .

Febrile neutropenia or neutropenia with infection	

Hold lenalidomide until resolution.

Thrombocytopenia: • Grade 3 (decrease to <50,000/ $\mu$ L) associated with > Grade 2 bleeding, OR • Grade 4 (decrease to <25,000/ $\mu$ L) with or without bleeding	

Hold lenalidomide.

-If platelet count < 50,000/<math>\mu</math>L for <math>\leq</math> 7 days, administer full dose of study treatment for the next cycle.

-If platelet count < 50,000/<math>\mu</math>L for <math>></math> 7 days, reduce the dose of lenalidomide by 1 dose level.

For subsequent episodes, dose reduction 2 of lenalidomide and drug discontinuation will be considered.

Grade 1 or 2 neutropenia and/or thrombocytopenia	

No dose reduction or delay.

Rash: • Any Grade desquamating (blistering), OR • Grade 4 non-blistering	

Discontinue lenalidomide.

Thromboembolic event $\geq$ Grade 3	

Hold lenalidomide.

Initiate therapeutic anticoagulation as clinically indicated, please evaluate interactions with other study drugs.

Resume lenalidomide without dose modifications at Day 1 of next cycle if benefit of therapy outweighs bleeding risk.

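### Table 3 has no hemorrhage rule for ibrutinib: after a first Grade 4 bleed attributed to it, the written guideline is re-dosing, at 560 mg if the bleed falls below Grade 2 in under 7 days and at 420 mg if slower

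*Combined protocol and SAP*

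**What the plan says.** Section 3.2 sets the planned exposure: "Ibrutinib 560 mg PO daily days 1-14", in 21-day cycles, for at most 6 cycles. Table 4 ("Table 4: Ibrutinib Dose Reduction") gives 420 mg and 280 mg as the two reduction steps.

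Table 3 in Section 3.3.3 has rows for neutropenia, febrile neutropenia, thrombocytopenia, low-grade cytopenias, gastrointestinal toxicity, atrial fibrillation or flutter, and a residual row, "Any other Grade 4 toxicity or unmanageable Grade 3 toxicity attributed to ibrutinib". Bleeding is named only in the thrombocytopenia row. There it qualifies the Grade 3 platelet trigger, which needs bleeding above the level in "Grade 2 bleeding, OR". The Grade 4 platelet trigger applies with or without bleeding.

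Both rows hold ibrutinib, and both have a branch ending "7 days, administer full dose of study treatment for the next cycle". In the thrombocytopenia row the branch depends on how long platelets stay below 50,000/µL. In the residual row it depends on how quickly the event improves. Slower recovery means one dose level down. Both rows close in the same way: "For subsequent episodes, dose reduction 2 of ibrutinib and drug discontinuation will be considered".

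The protocol recognizes the hazard. Section 4.1.9 links ibrutinib to bleeding, including serious intracranial hemorrhage. Section 1.2.8 reports one intracranial hemorrhage among more than 58 patients without CNS involvement treated with VIPOR.

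**The concern.** Every participant here has lymphoma in the CNS, and ibrutinib is the study drug that the protocol itself ties to intracranial bleeding. Yet an investigator who follows Table 3 as written after a first life-threatening bleed on ibrutinib is directed to hold and then re-dose. Neither applicable row treats the bleed as a reason to stop, and the thrombocytopenia row does not use the course of the bleed to choose the restart dose.

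The protocol writes firmer rules elsewhere. Table 5 says "Discontinue lenalidomide" for any blistering rash or a Grade 4 non-blistering one. Table 1 holds obinutuzumab for symptomatic bleeding whatever the platelet count. Ibrutinib has neither kind of rule for hemorrhage. What is at stake is renewed exposure to the suspected drug after such an event.

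**Working it through.** **1. Where a bleed lands in Table 3, and what follows a first episode**

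| Event | Row | Restart |
|---|---|---|
| Grade 4 bleed attributed to ibrutinib, no qualifying thrombocytopenia | Residual | 560 mg next cycle if below Grade 2 in under 7 days; 420 mg if over 7 days |
| Bleed above Grade 2 with Grade 3 thrombocytopenia, or any bleed with Grade 4 thrombocytopenia | Thrombocytopenia | 560 mg if platelets are under 50,000/µL for 7 days or less; 420 mg if longer |
| Grade 3 bleed judged manageable, platelets at or above 50,000/µL | None | No in-cycle hold trigger in Table 3 |

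The residual row reads below Grade 2 in under 7 days. The gastrointestinal row of Table 3, and the residual rows for venetoclax and lenalidomide, read Grade 2 or lower in 7 days or less. If that was the intent here too, return to full dose would be easier. Neither reading leads to a required stop.

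**2. Whether another section supplies the missing rule**

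- 3.3.1: a new cycle may not start while a drug-related toxicity is Grade 3 or higher, and delay of up to 6 weeks is allowed. This postpones re-dosing but does not bar it.
- 3.3.2: for non-hematologic toxicity, dosing may resume at Grade 1 or baseline. The text sits under venetoclax and obinutuzumab, so its reach to ibrutinib is arguable. It governs when dosing may resume, not whether the drug is stopped.
- 3.3.3: the tables are sample guidelines, to be revised at the investigator's discretion according to risk. This permits a stop.
- 3.8.1: removal for unacceptable adverse events refers back to 3.3. Investigator's discretion is listed separately. Both permit a stop.
- 4.2.5: ibrutinib is held when therapeutic anticoagulation is indicated. The trigger is anticoagulation, not a bleed.
- 4.2.6: ibrutinib is held around procedures. It does not address a bleed on treatment.

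None of these requires ibrutinib to stop after a major or intracranial bleed.

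**3. Exposure left open**

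- Planned doses: 6 cycles × 14 days = 84.
- First bleed in cycle 1: (6 − 1) × 14 = 70 further doses; 70/84 = 83.3%.
- First bleed in cycle 5: (6 − 5) × 14 = 14 further doses.
- Slow-recovery branch: the same number of doses at 420/560 = 75% of full dose.
- With a mandatory stop: 0.

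These are ceilings. They assume that all remaining cycles are given and that no second event occurs.

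**4. Could the situation arise in 10 participants? (illustration only)**

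Assume 1 intracranial hemorrhage in exactly 58 patients (the text says over 58) and the same rate in CNS lymphoma. The rate is 1/58 = 1.7%, with exact 95% interval 0.04% to 9.2%. The chance of at least one event in 10 participants is 1 − (1 − 1/58)^10 = 16%; at the interval limits it is 0.4% and 62%. This concerns a first event of any grade or cause. It says nothing about rebleeding on re-dosing.

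**The case against.** The strongest reply is that the protocol chose judgement over mandate. Table 3 is a sample guideline that investigators are told to adapt to risk. The team discusses each participant about weekly (7.4.1), and serious events go to the sponsor within 24 hours (8.3). Few clinicians would resume ibrutinib after an intracranial bleed without deliberation. Hold-and-judge is also an established pattern for serious events: Table 3 weighs restart after atrial fibrillation, and the Table 5 thromboembolic row says "Initiate therapeutic anticoagulation as clinically indicated, please evaluate interactions with other study drugs" and then allows lenalidomide to resume unreduced. All of this is true, and it limits how strongly the point can be put. But these provisions permit a stop without making it the default, and those two rows at least call for benefit to be weighed against risk. The rows that catch a bleed contain no such step after a first episode.

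A second reply concerns over-correction. Section 3.3 modifies only the most likely offending agent, and the residual row is limited to toxicity attributed to ibrutinib. A stop regardless of cause would remove ibrutinib after a procedural bleed or one due to another agent, against the dose-intensity argument in 4.2.1. That objection stands, and the fix is limited accordingly.

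A reader might infer that every intracranial bleed returns to full dose. It does not: in the residual row that branch needs improvement below Grade 2 in under 7 days, which an intracranial bleed may often fail to meet. A reader might also infer that 4.2.5 is contradictory. It speaks of continuing ibrutinib, but the next sentence plainly instructs a hold, so the operative rule is clear. Nor can a departure from labeling be shown, because Section 14.2.2 defers ibrutinib toxicities to a package insert outside these documents.

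**Conclusion.** The point holds in a limited form. Table 3 has no hemorrhage rule, and its written course after a first Grade 4 bleed attributed to ibrutinib is re-dosing at 560 mg or 420 mg, depending on recovery time. Under the thrombocytopenia row the choice depends on platelet duration alone. Other sections can delay or permit a stop; none requires it. The change is recommended, not essential to the validity of the trial.

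The size is an exposure count: up to 70 of 84 doses after a cycle 1 bleed, down to 14 after one in cycle 5. No rebleeding rate is available, so no probability of harm follows. The conclusion rests on reading Table 3 as the default that an investigator would follow unless exercising discretion.

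**What to change.** Add a hemorrhage row to Table 3:

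- For symptomatic intracranial hemorrhage, or any Grade 4 bleed, for which ibrutinib is judged a likely contributor, discontinue ibrutinib permanently, irrespective of platelet count.
- Exclude these events from the return to full dose in both the residual row and the thrombocytopenia row.
- Keep bleeds clearly due to another cause, such as a procedure or another agent, under the offending-agent rule of 3.3. Hold ibrutinib until the bleed resolves, and document a benefit-risk review before restart.
- Continue the other drugs under 3.3.1.

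No change to 4.2.5 or Table 5 is needed.

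The cost is a protocol amendment to one table, with no added visits or tests. A rare affected participant loses up to 70 planned ibrutinib doses, against the view in 4.2.1 that even brief holds may harm efficacy. The stop also counts toward the rule in 3.3.1 that two discontinued drugs end treatment. Alone it does not end treatment. Together with a second drug stopped for toxicity within the first 2 cycles, it could make that participant a failure on the primary endpoint (10.4.2).
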